### **AEs with Special Interest**

A list of preferred terms that are to be combined for the assessment of each of the pre-specified adverse events (including Extrapyramidal Symptoms (EPS)-related AEs, metabolic-related AEs, hypersensitivity-related AEs, and suicidality and self-injury related AEs) is provided in [Attachments 4.5.1 - 4.5.4](#). These AE preferred terms are determined and verified by medical review of coded AE terms during data review meeting and finalized prior to database lock. The incidence and exposure adjusted incidence rates of EPS-related AEs, metabolic-related AEs,

hypersensitivity-related AEs, and suicidality and self-injury related AEs will be summarized by analysis group and by analysis subgroup, respectively. In addition, EPS-related AEs will be summarized for akathisia and non-akathisia event as well.

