14.7.4.2. Safety Evaluation

All safety evaluations will be summarized for all subjects by analysis group for the safety population.

Safety evaluations include:

- AEs, SAEs, Discontinuation due to AEs and SAEs;
- Laboratory safety tests (chemistry, including liver function tests and bilirubin; hematology including HbA_{1c}; serum lipids; glucose; hormonal parameters; and urinalysis);
- Body weight, height, BMI, waist circumference, vital signs, physical examinations, and ECG parameters;
- Simpson-Angus Scale (SAS);
- Barnes Akathisia Rating Scale (BARS);
- Abnormal Involuntary Movement Scale (AIMS);
- Tanner staging, and menstrual cyclicity (female subjects).

For subjects continued from Study D1050301 and D1050326:

- Columbia Suicide Severity Rating Scale (C-SSRS);
- CogState Cognitive Test Battery;
- Udvalg for Kliniske Undersøgelser Side Effect Rating Scale (UKU).

For subjects continued from Study D1050326:

- Young Mania Rating Scale (YMRS) score.

The primary analysis for the study is to assess the incidence of AEs, SAEs, and discontinuations due to AEs. The terms used in the eCRFs by investigators to identify adverse events will be coded using the Medical Dictionary for Regulatory Activities (MedDRA). All reported adverse events with onset on or after the first dose of study drug during the treatment phase (ie, treatment-emergent adverse events) will be included in the analysis.

AEs will be summarized by presenting the number and percentage of subjects having any AE, having an AE by body system, and having each individual AE. The incidence of an AE is determined by occurrence of at least one AE regardless of the frequency, severity and/or relationship to study medications. AEs will also be summarized by maximum severity and relationship to study medication (as assessed by the investigator), and action taken.

Special attention will be given to those subjects who discontinue treatment due to an adverse event, or who experienced a severe or a serious adverse event (eg, summaries, listings, and narrative preparation may be provided, as appropriate).

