### **2.6.4. Adverse Events**

A treatment-emergent adverse event (TEAE) is defined as an AE onset on or after the start of open-label treatment period through 7 days after study drug discontinuation (14 days for serious adverse events and deaths). For sake of simplicity, hereafter TEAE is referred as AE in the section.

The overall incidence (ie, number and percent of subjects with one or more AE in each category) of AEs, serious AEs, deaths, AEs leading to discontinuation, drug-related AEs, serious drug-related AEs, drug-related AEs leading to discontinuation, serious AEs leading to discontinuation, and serious drug-related AEs will be summarized by analysis group and by analysis subgroup, separately.

AEs by system organ class (SOC) (number and proportion of subjects with one or more AEs within a system organ class) will be summarized by analysis group. For each AE, the percentage of subjects who experienced at least one occurrence of the given event will be provided by preferred term, grouped by system organ class, and presented by analysis group and by analysis subgroup. AEs for age subgroup summary will be also presented by SOC and preferred term and by analysis group and analysis subgroup.

Furthermore, additional summaries will be created based on the following combined preferred terms:

- Dystonia - preferred terms: dystonia, trismus, oculogyric crisis, oromandibular dystonia, tongue spasm, torticollis
- Parkinsonism - preferred terms: bradykinesia, drooling, extrapyramidal disorder, glabellar reflex abnormal, hypokinesia, parkinsonism, psychomotor retardation
- Somnolence - preferred terms: hypersomnia, sedation, somnolence, hypersomnolence

According to MedDRA coding guidelines for Lurasidone pediatric program,

- EPS-related reported terms for Tremor, Rigidity or Muscle Rigidity will be queried for further specificity. Sites will qualify if the reported term is Parkinsonian or non-Parkinsonian in nature; if confirmed, the reported term will be coded to lowest level terms of Parkinsonism; if not, the term will be coded to specific symptom.
- For reported term Restlessness, sites will qualify if the reported term is Akathisia or non-Akathisia in nature; if confirmed, the reported term will be coded to lowest level terms of Akathisia; if not, the term will be coded to specific symptom.

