### **AEs by Exposure**

The TEAEs will be summarized by exposure to study drug using time intervals beginning with the earliest concurrent exposure to study drug for following AE summary as needed.

Denominators for exposure intervals will be based on the number of subjects who were exposed as of the first day of the interval; for cases where events meet the treatment-emergent definition but start after the last dose, the exposure interval for the event will be considered the interval of the last day of exposure to study medication.

- AEs by system organ class (SOC) and preferred term, Serious AEs by SOC and preferred term, and AEs leading to discontinuation by SOC and preferred term (sorted alphabetically by SOC and preferred term within SOC).
- AEs by preferred term, AEs with special interest by preferred term (sorted by descending order per frequency count)

Exposure category to be assessed is given below:

- Exposure categories : 1-13 days, 14-27 days, 28-55 days, 56-83 days, 84-167 days, 168-363, and  $\geq 364$  days.

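### The headline AE, SAE and AE-discontinuation summaries are percentages with no exposure-adjusted rate, and the only exposure-based view of them is an optional interval table with no stated any-event row

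*SAP*

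**What the plan says.** Protocol 14.7.4.2 names the main result: "The primary analysis for the study is to assess the incidence of AEs, SAEs, and discontinuations due to AEs". SAP 2.6.4 sets the metric: "The overall incidence (ie, number and percent of subjects with one or more AE in each category) of AEs, serious AEs, deaths". The list goes on to discontinuations caused by AEs and to related categories, by analysis group and by analysis subgroup. SAP 2.6.1 bases all safety summaries on the safety population, so the denominator is everyone treated. SAP 2.1.9 gives each core-study cohort its own column and adds a combined one.

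Under AEs with Special Interest, SAP 2.6.4 adds a rate for four groups of events only: "The incidence and exposure adjusted incidence rates of EPS-related AEs, metabolic-related AEs", and the same for hypersensitivity and for suicidality or self-injury. It gives no formula for the rate.

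The next subsection, AEs by Exposure, also reaches the primary variables. It lists AEs by system organ class and preferred term, then "Serious AEs by SOC and preferred term, and AEs leading to discontinuation by SOC and preferred term". It uses an at-risk denominator: "Denominators for exposure intervals will be based on the number of subjects who were exposed as of the first day of the interval". The intervals are "1-13 days, 14-27 days, 28-55 days, 56-83 days, 84-167 days, 168-363, and" a final one open from day 364. The commitment is weak, with intervals "beginning with the earliest concurrent exposure to study drug for following AE summary as needed".

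**The concern.** Subjects may stay for a few days or for 104 weeks, and the plan itself expects about 30% to leave in the first six months. A percentage of all treated subjects then mixes two things: how often events occur and how long subjects were watched. For the same underlying event rate, a group that leaves sooner shows a lower percentage. The same applies when the figure is set beside a study of different length.

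The SAP recognizes this for special-interest AEs but does not carry it to the variables the protocol calls primary. What is at stake is how the main long-term safety numbers are read. No hypothesis is tested, so no error rate is involved.

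**Working it through.** **Figures in the documents.** Enrolment: 271 + 125 + 306 = 702, which matches the synopsis. Six-month exposure in the first two cohorts: (271 + 125) × (1 − 0.30) = 277, above the stated floor of 100. Both figures reproduce. Attrition of about 30% over six months is in Protocol 14.5 and SAP 1.2.1; the 104-week duration is in the synopsis.

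**Assumptions, not in the documents.** Constant dropout and event hazards; event hazard h = 0.10 per year; attrition of 20% and 45% as alternatives to 30%; 104 weeks taken as 2 years.

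**Retention at 30%.** Dropout hazard λ = −ln(0.70)/0.5 = 0.7133 per year.
- Remaining at 1 year: 0.70² = 49%. At 2 years: 0.70⁴ = 24%, or about 169 of 702.
- Mean exposure: (1 − 0.2401)/0.7133 = 1.07 years, so about 748 of 702 × 2 = 1404 possible person-years.

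**Crude percentage.** Crude = h/(h + λ) × (1 − exp(−2(h + λ))).

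| Attrition per 6 months | λ | Crude | Person-years to first event or dropout, per subject | Rate per 100 |
|---|---|---|---|---|
| 20% (assumed) | 0.4463 | 0.1831 × 0.6646 = 12.2% | 0.6646/0.5463 = 1.217 | 10.0 |
| 30% (plan) | 0.7133 | 0.1229 × 0.8034 = 9.9% | 0.8034/0.8133 = 0.988 | 10.0 |
| 45% (assumed) | 1.1957 | 0.0772 × 0.9251 = 7.1% | 0.9251/1.2957 = 0.714 | 10.0 |

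With full follow-up the two-year risk is 1 − exp(−0.20) = 18.1%. At 30% attrition the percentage is 8.2 points lower, about 45% of that risk.

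**How much the interval table recovers.** At 30% attrition its denominators would be about 702, 684, 666, 631, 597, 507 and 345 at the starts of the seven intervals. Within an interval of w years the percentage is h/(h + λ) × (1 − exp(−w(h + λ))), counting first events among subjects event-free at its start. Comparing 20% with 45% attrition:
- Overall percentage: 12.2% against 7.1%, ratio about 1.7.
- Days 84–167 (w = 0.230): 2.16% against 1.99%, ratio 1.09.
- Days 168–363 (w = 0.537): 4.65% against 3.87%, ratio 1.20.
- Day 364 on (w = 1.0): 7.70% against 5.60%, ratio 1.37.

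The table removes most of the dependence on retention in the first year and less of it in the second.

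**The case against.** The strongest reply is that AEs by Exposure already does this work. It covers the same three event types, and subjects who have left drop out of the denominator. The interval ratios bear this out for the first year. A reader might infer from the headline tables that the primary variables have no exposure-based summary, or that the interval table is just as dependent on retention. The SAP supports neither reading. What the table leaves open is narrower: it is conditional, it is listed by organ class and preferred term with no overall row stated, it does not say how subjects with an earlier event are counted, and its last interval holds the whole second year.

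Second, the stated objective (Protocol 5.2, SAP 1.1) is the proportion of subjects with events. The cohorts are different diseases and ages, and the protocol rules out statistical comparison of treatment groups. This stands as a reason to keep the percentages. It does not make them independent of follow-up, even within one cohort.

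Third, exposure is disclosed elsewhere: treatment duration by group and subgroup (SAP 2.2.2.4), and disposition with a Kaplan-Meier plot of early discontinuation (SAP 2.2.2.2). A reader could form a rough rate by hand. However, the duration categories also stop at 364 days or more, and the plot is for discontinuation of any cause.

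Fourth, a single rate is not neutral either. If events cluster early, a group followed longer shows a lower rate. This stands and shapes the fix.

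**Conclusion.** The point holds in a limited form. The three primary safety variables have no planned person-time rate, and their only exposure-based summary is optional and has no stated overall row. At the plan's own attrition, held constant over two years, and an assumed 0.10 events per year, the reported figure would be 9.9% where the full-follow-up risk is 18.1%.

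The 12.2% and 7.1% figures show sensitivity to retention only. A reader might infer from them that one cohort will look safer than another. The documents do not support that: they give one attrition figure, none by cohort, and if it applied equally to all three the illustrated distortion between cohorts would be zero. A reader might also infer that the SAP already contains a rate method that can simply be reused. It names the rate but does not define it.

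This is a worthwhile improvement to a descriptive plan; it does not invalidate the planned summaries.

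**What to change.** In SAP 2.6.4, for the lock 2 analysis and the full clinical study report:

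1. Keep the number and percent of subjects. Beside them add subjects with event per 100 patient-years for any TEAE, SAEs and AEs leading to discontinuation, by analysis group and subgroup.
2. Write the person-time definition once: from the start of the open-label treatment period (SAP 2.1.2) to the first event, or otherwise to the end of the TEAE window (7 days after study drug discontinuation; 14 days for serious events and deaths). Apply it to the special-interest AEs too.
3. Make the AEs by Exposure table mandatory for these three event types, with an any-event row and a stated rule for subjects who had the event earlier. It belongs beside the rate because a single rate assumes a roughly constant hazard, and events that cluster early need the interval view.

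Exposure and onset dates are already collected. Lock 1 and the schizophrenia report are complete, but the SAP describes lock 2 and the full report on all subjects as still to come. The cost is a few extra table rows and a short definition.

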### **AEs by Exposure**

The TEAEs will be summarized by exposure to study drug using time intervals beginning with the earliest concurrent exposure to study drug for following AE summary as needed.

Denominators for exposure intervals will be based on the number of subjects who were exposed as of the first day of the interval; for cases where events meet the treatment-emergent definition but start after the last dose, the exposure interval for the event will be considered the interval of the last day of exposure to study medication.

- AEs by system organ class (SOC) and preferred term, Serious AEs by SOC and preferred term, and AEs leading to discontinuation by SOC and preferred term (sorted alphabetically by SOC and preferred term within SOC).
- AEs by preferred term, AEs with special interest by preferred term (sorted by descending order per frequency count)

Exposure category to be assessed is given below:

- Exposure categories : 1-13 days, 14-27 days, 28-55 days, 56-83 days, 84-167 days, 168-363, and  $\geq 364$  days.

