A Data and Safety Monitoring Board (DSMB) will review safety and clinical outcome data including data on adverse events (AEs) and serious adverse events (SAEs) at regular intervals until the D1050301, D1050325, and D1050326 studies are complete and as long as necessary for the D1050302 study, as determined by the Sponsor. The DSMB will be independent of the Sponsor, contract research organization (CRO), and the investigators and will be empowered to recommend stopping the study due to safety concerns, but not for efficacy or futility. The membership of the DSMB and its mandate is denoted in the DSMB charter.
Number of Subjects (planned): The estimated number of subjects eligible for enrollment is approximately 702 subjects.
Diagnosis and Main Criteria for Inclusion:
Subject has completed Study D1050301 (Visit 9), Study D1050325 (Visit 9), or Study D1050326 (Visit 8); is judged to be appropriate for long-term treatment with lurasidone; has provided informed assent/consent (where developmentally appropriate); and has met all other entry criteria.
Investigational Product, Dosage and Mode of Administration: Subjects will receive lurasidone (lurasidone HCl) administered orally, 20, 40, 60 or 80 mg (flexibly dosed), once daily in the evening with food (at least 350 calories) or within 30 minutes after eating.
Duration of Treatment: 24 months (104 weeks)
Reference Therapy, Dosage and Mode of Administration: Not applicable
Criteria for Evaluation:
Safety Assessments:

Name of Sponsor/Company: Sunovion Pharmaceuticals Inc.
Name of Investigational Product: Lurasidone (lurasidone HCl)
All Subjects:

 Treatment-emergent adverse events (TEAEs), TEAEs leading to discontinuation and serious AEs (SAEs); Laboratory tests, vital signs, body weight and body mass index (BMI), waist circumference, physical examination, height (as measured by stadiometer), electrocardiogram (ECG), hormonal parameters; Movement disorders as assessed by Abnormal Involuntary Movement Scale (AIMS), Barnes Akathisia Rating Scale (BARS), and the Simpson-Angus Scale (SAS); Tanner staging, and menstrual cyclicity (female subjects).
For subjects continued from Study D1050301 and D1050326:

 Columbia Suicide Severity Rating Scale (C-SSRS); CogState Computerized Cognitive Test Battery; Udvalg for Kliniske Undersogelser Side Effect Rating Scale (UKU).
For subjects continued from Study D1050326:

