### **1.2.1. Determination of Sample Size**

Subjects who complete the respective double-blind studies D1050301, D1050325 or D1050326, sign the consent, and meet all entry criteria are included in this study. Studies D1050301, D1050325, and D1050326 have finished, with a total of 271 subjects from D1050301, 125 subjects from D1050325, and 306 subjects from D1050326 enrolling into D1050302. Based on an estimated attrition rate of approximately 30% of subjects over six months, it is expected that at least 100 subjects are to be exposed to lurasidone for a minimum of 6 months for subjects continued from studies D1050301 and D1050325 in study D1050302.

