#### **2.2.2.4. Extent of Exposure**

Treatment duration is defined as the amount of elapsed time between the first and the last day that study medication was taken (inclusive). It will be calculated (in days) in terms of the

difference in relative study days between the last and first dose of study medication, plus one day. If the end date of the medication intake is unknown for subjects who either completed or early terminated the study (eg, subject is lost to follow-up), it will be imputed as the earlier of the disposition date (ie, date of the last contact with subject) and 14 days from the date that the last medication kit is dispensed if the last contact visit is either V1E (OL baseline), V2E (W2), V3E (W4) , or V4E (W6), and 28 days from the date that the last medication kit is dispensed is V5E (W8) or after.

Descriptive statistics (N, mean, standard deviation, median, and range) will be presented by analysis group and analysis subgroup for treatment duration. Number of subjects with duration in each of following categories (days):  $\geq 14$ ,  $\geq 28$ ,  $\geq 56$ ,  $\geq 84$ ,  $\geq 112$ ,  $\geq 140$ ,  $\geq 168$ ,  $\geq 196$ ,  $\geq 252$ ,  $\geq 308$ , and  $\geq 364$ ; 1-13, 14-27, 28-55, 56-83, 84-111, 112-139, 140-167, 168-195, 196-251, 252-307, 308-363,  $\geq 364$  days will also be presented. Return of the blister card at any given visit is not a prerequisite for inclusion in exposure summary statistics if corresponding dose start and end dates are reported.

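### The AE-by-exposure table divides by a head count over intervals of 13 to about 365 days, so its percentages are not comparable across intervals of different width and year 2 is not resolved in time

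*SAP*

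**What the plan says.** The AEs by Exposure part of SAP 2.6.4 plans, as needed, summaries by time on drug of all TEAEs, serious AEs, AEs leading to discontinuation and special-interest AEs. It gives three rules.

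- Denominator: "Denominators for exposure intervals will be based on the number of subjects who were exposed as of the first day of the interval".
- Intervals: "Exposure categories : 1-13 days, 14-27 days, 28-55 days, 56-83 days, 84-167 days, 168-363, and" a last class of 364 days or more.
- A treatment-emergent event that starts after the last dose: "the exposure interval for the event will be considered the interval of the last day of exposure to study medication".

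The section specifies no person-time, rate or width adjustment. It does not say whether a subject with a recurrence counts again in a later interval. The word percentage is not used there, but a stated denominator implies one.

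The Protocol synopsis sets the treatment period: "Duration of Treatment: 24 months (104 weeks"). The duration categories in SAP 2.2.2.4 also end in an open class at 364 days.

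Three related provisions lie nearby. The special-interest paragraphs of SAP 2.6.4 plan exposure-adjusted incidence rates for four AE classes, not stated by interval. The treatment-emergent mania paragraphs give frequencies for the first 52 weeks and for the whole period, for D1050326 subjects. SAP 2.2.2.2 plans a Kaplan-Meier plot, for early discontinuation only.

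**The concern.** A percentage of those exposed at the start of an interval rises with the length of the interval even when the risk per day is constant. The longest interval here is about 28 times the shortest (365/13 = 28.1). A reader going along a row would tend to see late-emerging risk where there is none, or miss an early risk that fades.

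The primary objective is long-term safety, and the 104-week duration is justified by the wish to see longer-term effects. The second year is nevertheless one cell, so the table cannot show whether events cluster at 13 months or at 23.

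**Working it through.** **Inputs from the documents.** Enrolment is "271 subjects from D1050301, 125 subjects from D1050325, and 306 subjects from D1050326 enrolling into D1050302", that is 271 + 125 + 306 = 702, which matches the Protocol synopsis. Attrition is "Based on an estimated attrition rate of approximately 30% of subjects over six months". The plan's own expectation can be reproduced: (271 + 125) × 0.70 = 277, which satisfies its lower bound of 100 subjects with six months' exposure. Interval lengths are 13, 14, 28, 28, 84 and 196 days, and Days 364 to 728 make 365.

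**Assumptions.** Attrition is exponential: d = −ln(0.70)/182 = 0.00196 per day, about 0.716 per year. The AE hazard h is constant. The documents give none, so 0.02 to 2.0 per year is shown.

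**Formulas.** For an interval of length L that starts s days after Day 1, among subjects exposed at its start:

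- subject can count again in later intervals: h/(h+d) × [1 − exp(−(h+d)L)]
- first-ever onset only, same denominator: the same expression × exp(−h s)

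**Results.** Expected percentages at constant risk, with 30% attrition per six months:

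| h per year | Counting | 1–13 | 14–27 | 28–55 | 56–83 | 84–167 | 168–363 | ≥364 | Last/first |
|---|---|---|---|---|---|---|---|---|---|
| 0.02 | again | 0.07 | 0.08 | 0.15 | 0.15 | 0.42 | 0.89 | 1.42 | 20 |
| 0.02 | first | 0.07 | 0.08 | 0.15 | 0.15 | 0.42 | 0.88 | 1.39 | 20 |
| 0.10 | again | 0.35 | 0.38 | 0.74 | 0.74 | 2.10 | 4.35 | 6.83 | 19.5 |
| 0.10 | first | 0.35 | 0.38 | 0.74 | 0.73 | 2.05 | 4.15 | 6.19 | 17.6 |
| 0.5 | again | 1.74 | 1.87 | 3.66 | 3.66 | 10.03 | 19.71 | 28.92 | 16.6 |
| 0.5 | first | 1.74 | 1.84 | 3.53 | 3.39 | 8.95 | 15.68 | 17.60 | 10.1 |
| 1.0 | again | 3.45 | 3.71 | 7.18 | 7.18 | 19.00 | 35.07 | 47.79 | 13.8 |
| 1.0 | first | 3.45 | 3.58 | 6.67 | 6.18 | 15.14 | 22.20 | 17.69 | 5.1 |
| 2.0 | again | 6.79 | 7.28 | 13.84 | 13.84 | 34.21 | 56.50 | 68.76 | 10.1 |
| 2.0 | first | 6.79 | 6.78 | 11.94 | 10.24 | 21.71 | 22.64 | 9.42 | 1.4 |

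Ratios use unrounded percentages.

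**Sensitivity to attrition.** At 0.10 per year, counting again, the ratio is about 23 at 15% attrition per six months and about 15 at 50%. With no dropout it is [1 − exp(−0.10 × 365/365.25)] / [1 − exp(−0.10 × 13/365.25)] = 0.0951/0.00355 = 26.8.

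**A falling hazard.** With hazards of 0.40, 0.40, 0.30, 0.30, 0.20, 0.15 and 0.10 per year across the seven intervals, counting again, the table would read 1.40, 1.50, 2.21, 2.21, 4.15, 6.44 and 6.83%. The true rate falls four-fold while the percentages rise almost five-fold (6.83/1.40 = 4.9).

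**Check of the remedy.** At 0.10 per year, with person-time running to the first event in the interval, dropout or the interval's end, the first interval expects 2.46 subjects with an event in 24.6 person-years. The last expects 23.55 in 235.5. Both give 10.0 per 100 person-years, as do the other five.

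**Numbers in year 2.** Expected to enter Day 364: 702 × exp(−0.00196 × 363) = about 345, staying a mean of [1 − exp(−365d)]/d = about 261 days in the class. Expected to enter Day 546: 702 × exp(−0.00196 × 545) = about 241 (242 if six months is taken as half of 365.25 days).

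**The case against.** Several points on the other side are sound.

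- **Size.** A reader might settle on one figure, such as the 17-fold rise at 0.5 per year. The documents do not support a single number: they give no hazard and no counting rule. Elsewhere SAP 2.6.4 counts subjects with at least one occurrence, and under first onset only the ratio at 0.5 per year is about 10. For very common events the steep rise largely disappears, and at 2.0 per year the last interval falls below the one before it.
- **Use of the table.** One might infer that comparison across intervals is its only purpose. The SAP does not say so. Summary tables are presented by analysis group and subgroup (SAP 2.1.9), and reading across groups within one interval is not distorted by unequal widths. Adjacent intervals of 13 and 14 days, or 28 and 28, are also close to comparable.
- **Other time displays.** One might infer that this is the only AE display by time. Treatment-emergent mania has 52-week and overall summaries, and SAP 2.1.7 does the same for abnormal laboratory, vital-sign and ECG values.
- **Last class.** One might infer that the table stops at Day 364. It is open-ended, so second-year events are included.
- **Existing safeguards.** Dropout before each interval is handled. Person-time rates are already planned for EPS, metabolic, hypersensitivity and suicidality AEs. SAP 2.2.2.4 gives summary statistics of treatment duration and SAP 2.2.2.2 a Kaplan-Meier plot of discontinuation, so second-year retention can be seen.
- **Weight.** The study is descriptive, the table is planned only as needed, and its labels show the widths.

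These points limit the size and scope of the concern. They do not repair the table: the special-interest rates are not by interval, the mania summaries cover one outcome in one cohort, and seeing the widths does not give a reader the person-time needed to correct for them.

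**Conclusion.** The concern holds as a limited, inexpensive improvement. The planned denominator leaves percentages that cannot be compared across intervals of different width, and it places second-year events in one undivided class. At constant risk and the plan's attrition, the last-to-first ratio is about 20 to 10 over hazards of 0.02 to 2.0 per year if subjects can count again. With first onset only it is about 20 at 0.02, 10 at 0.5, 5 at 1.0 and 1.4 at 2.0 per year.

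These figures rest on assumed hazards, exponential dropout that is independent of AEs, and treatment running to Day 728. The direction of the distortion is secure for uncommon and moderately common events; its size is not. No planned statistical test is affected.

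**What to change.** In the AEs by Exposure part of SAP 2.6.4:

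1. Keep the planned counts and denominators.
2. Add, for each interval, the person-years accrued in it and the number of subjects with an event (or events) per 100 person-years.
3. State whether only first onset or every recurrence is counted, and define person-time to match. Because events after the last dose go to the last exposure interval, say whether the post-dose days count as person-time.
4. Split the class of 364 days or more, for example into 364–545 and 546 days or more.

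A matching split of the duration categories in SAP 2.2.2.4 is optional. It is mainly presentation, given the duration statistics and Kaplan-Meier plot already planned.

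The cost is SAP wording and modest programming with dates already collected. Late cells become sparser: under the plan's attrition about 345 of 702 subjects would enter at Day 364 and about 241 to 242 at Day 546, before division by analysis group.
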